10.2 Recruitment and consent

Due to the fact that Dutch guidelines request that a colorectal cancer patient should be operated within 5 weeks after the positive result from the lab, the timelines for recruitment and informed consent are short to allow enough time for training. Patients will be given information about the study via the research subject information leaflet by the gastroenterologist if after colonoscopy the patient is highly suspected for having colon cancer (95% certainty). After confirmation of cancer diagnosis, his/her permission is requested to be contacted about the study by the researcher. The researcher will contact the patient to answer any questions that he/she might have and ask if the patient is willing to participate in the trial. The patient information letter and informed consent are provided in the attachments of the study dossier. The right of a patient to refuse participation without giving reasons will be respected. The patient will remain free to withdraw at any time from the study without consequences for further treatment. In case of a positive answer, a first meeting will be scheduled at the sports physician. The sport physician will obtain the written informed consent prior to the first baseline measurements. During the first baseline measurements the patient will be randomized using Research Manager. After the measurements, the patient is informed about the result of the randomization. Patients are informed that their data is coded, and will be stored for 15 years before destruction.

The independent doctor available for patients is dr. [name] ([name])

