AZIENDA USL DI FERRARA – AZIENDA OSPEDALIERO-UNIVERSITARIA DI FERRARA
DIPARTIMENTO INTERAZIENDALE DI CHIRURGIA
U.O. CHIRURGIA GENERALE DELTA – ARGENTA – U.O. CHIRURGIA 1 – U.O. CHIRURGIA 2

Studio Randomizzato Controllato sulla PREABILITAZIONE – Diagramma di Flusso							
	Preoperatorio			Chirurgia	Postoperatorio		
Settimane	-5	-4	-1	0	4	8	52
Case manager	Adesione Inclusione	Basale HRQoL QoL SF-36 GAD-7 PHQ-9	Preoperatorio HRQoL QoL SF-36 GAD-7 PHQ-9	Chirurgia x	Follow up 30 giorni HRQoL QoL SF-36 GAD-7 PHQ-9	Training 8 settimane HRQoL QoL SF-36 GAD-7 PHQ-9	Follow up 1 anno HRQoL QoL SF-36 GAD-7 PHQ-9
Medico dello sport	x	Consenso Informato VO2max Soglia Anaerobica Exercise-ECG 1RM* 6MWT Sit-to-stand test	Consenso Informato VO2max Soglia Anaerobica Exercise-ECG 1RM* 6MWT Sit-to-stand test	x	VO2max Soglia Anaerobica Exercise-ECG 1RM* 6MWT Sit-to-stand test	VO2max Soglia Anaerobica Exercise-ECG 1RM* 6MWT Sit-to-stand test	x
Nutrizionista/ Dietista		Diario dietetico Altezza, peso Calo ponderale % # Circonferenza polso/addome/avan braccio Plica del tricipite Forza presa mano PG-SGA score	Diario dietetico Altezza, peso Calo ponderale % # Circonferenza polso/addome/avan braccio Plica del tricipite Forza presa mano PG-SGA score	x	Altezza, peso Calo ponderale % Forza presa mano PG-SGA score	Altezza, peso Calo ponderale % Forza presa mano PG-SGA score	x
Anestesista	x	x	Visita preoperatoria	ERAS**		x	x
Chirurgo	Informazione Adesione	x	ERAS**	x	Dati ambulatoriali	x	x
Ricercatore	x	x	x	x	Morbilità-mortalità a 30 giorni	Morbilità-mortalità a 60 giorni	Mortalità a 1 anno

* Diverse misurazioni 1RM effettuate mediante: leg press, abdominal crunch, chest press and lateral pull down. ** Linee Guida Enhanced Recovery After Surgery (ERAS) . # calo ponderale negli ultimi 3--6 mesi

AZIENDA USL DI FERRARA – AZIENDA OSPEDALIERO-UNIVERSITARIA DI FERRARA
DIPARTIMENTO INTERAZIENDALE DI CHIRURGIA
U.O. CHIRURGIA GENERALE DELTA – ARGENTA – U.O. CHIRURGIA 1 – U.O. CHIRURGIA 2

- La fase di Adesione (– 5 settimane): nella nostra realtà viene condotta dal Chirurgo alla prima visita pre-operatoria.
Il Nutrizionista/dietista può impostare il diario dietetico

- Nella fase Basale (– 4 settimane): il Medico dello Sport/Fisiatra somministrano il consenso informato alla fase di preabilitazione ed effettuano contemporaneamente i test ergometrici e la prima seduta di allenamento
Il nutrizionista può effettuare le misurazione antropometriche

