5. TREATMENT OF SUBJECTS

5.1 Investigational product/treatment

1. Patient triage medical conditions

Patient triage will allow us to tailor perioperative management, which may lower the risk for postoperative complications 30% in 'the risky' group. An anaerobic threshold (AT) value of the VO₂max test of 10 ml/kg/min gives 0.88 specificity and 0.79 sensitivity with area under curve of 0,85 for risk of complications.⁵³ Also severe pulmonary and cardiac disease will often be detected and scaled upon severity with exercise testing.

Triage will also focus on anemia, to identify patients' cardiopulmonary comorbidity using VO₂ peak tests. Patients will be screened preoperatively (4 weeks before surgery) to capture insufficient hemoglobin levels (thresholds in Canada: >11.2 g/dl, Europe: >7mmol/l). In case of iron insufficiency, hemoglobin levels will be optimized using iron injections. In combination with training it may give substantial effect.

Triage described above will be applied to the intervention group as well as controls.

2. Prehabilitation intervention

The intervention described below will only be given to the intervention arm of this study. The only exception is the smoke-cessation program, which will be offered to all patients.

Exercise program

An exercise specialist (kinesiologist, sport physician) will assess patients' mobility and capacity to undertake exercise. All participants will undergo a cardiopulmonary exercise test (CPET) and the exercise intensity will be defined and personalized on the individual CPET values. Based on the evaluation, a personalized program from the standardized program will be coordinated, as defined in appendix II. Additional to the preoperative exercise program, patients will receive information regarding breathing techniques to prevent occurrence of pneumonia.

With the intervention we try to achieve a maximum training stimulus in combination with a recovery diet, in order to achieve these goals in 4 weeks.

The program exists of several components:

- Strength training and high intensity interval training: this will be done 3 times a week supervised in the hospital. The strength training consists of 2 series of 10 repetitions of 6 exercises targeting all major muscle groups. The high intensity interval training aimed at 90% of the VO₂-peak
- Homework endurance training (low to moderate intensity): 4 times a week done at home.

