8.2 Randomization, blinding and treatment allocation

Patients will be randomized by block randomization with a block size of 8, with a 1:1 allocation by means of randomization software, stratified by study sites, neoadjuvant therapy vs. no neoadjuvant therapy and tumour location (colon/rectum). Patients will be allocated either to the prehabilitation intervention group, receiving 4 weeks prehabilitation, or to the control group, receiving no prehabilitation (standard care). Both groups will receive 8-week rehabilitation following the current international ERAS guidelines. Similarly all the perioperative care will follow the ERAS guidelines for colorectal surgery.

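### Randomisation takes place during the baseline measurements with nothing keeping test staff unaware of the arm, and a single block size of 8 is printed in the protocol

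*Protocol*

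**What the plan says.** Protocol section 10.2 gives the order of events at the first visit:

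- Consent: "The sport physician will obtain the written informed consent prior to the first baseline measurements".
- Allocation: "During the first baseline measurements the patient will be randomized using Research Manager".
- Disclosure: "After the measurements, the patient is informed about the result of the randomization".

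Section 8.2 gives the method: "Patients will be randomized by block randomization with a block size of 8", 1:1, by software, stratified by site, neoadjuvant therapy and tumour location. Its heading names blinding, but the text masks nobody. The arms are four weeks of prehabilitation or none.

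Section 4.3 excludes patients who cannot exercise or do the 6MWT, and those with conditions that contraindicate exercise. Section 5.1, on triage of both arms, says that "severe pulmonary and cardiac disease will often be detected and scaled upon severity with exercise testing".

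The Ferrara flow-chart page at the front says of the baseline phase that the sports physician or physiatrist obtain consent to prehabilitation and "effettuano contemporaneamente i test ergometrici e la prima seduta di allenamento", that is, carry out the exercise tests and the first training session together.

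**The concern.** Two features weaken concealment.

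The first is timing. If the allocation exists while baseline testing is under way, a member of staff who knows it may encourage one arm differently in an effort-dependent test. The 6MWT is self-paced with staff encouragement (8.3), and its baseline value is one of the repeated measurements in the analysis of the second primary outcome (9.6). Section 4.4 also frames the 6MWT effect as a proportion improved, which needs a baseline. The same knowledge could colour a borderline judgement on whether exercise is contraindicated, if that judgement is still open when the arm is known.

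The second is predictability. With one known block size and arms that become visible once treatment starts, the last allocations in a block can be worked out from the earlier ones. That could influence who is approached next.

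The Comprehensive Complication Index has no baseline value, so only selection at entry, not the baseline tests, could touch it.

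**Working it through.** **Sequence at the visit**

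1. Section 10.2 gives consent, then the start of measurements, then randomisation during them, then disclosure to the patient after them. The patient's own effort is protected; staff knowledge is not addressed.
2. Appendix I gives the 6MWT and 1-RM to the physiotherapist, the exercise test to the sport physician, and inclusion to the researcher or case manager. Section 10.2 does not say who randomises or who sees the result.
3. Sections 4.3 and 5.1 together mean that the baseline exercise test can supply information bearing on an exclusion criterion. Section 10.4 also expects more cardiopulmonary conditions to be found. No sentence requires the tests to be complete before allocation.
4. If the contrast is change from baseline, a shift of x metres in one arm's baseline moves that contrast by x metres in the opposite direction. A plain comparison of 8-week values would not move. The protocol gives no basis for choosing x.

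**Predictability of the block**

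The total of 708 (4.4) is not in dispute. With a difference of 0.30 × 10.4 = 3.12 and SD 14, a two-sided t-test at 0.05 with 80% power needs 318 per arm. Then 318 / 0.9 gives 354 per arm, 708 in all.

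1. Strata: 6 sites × 2 × 2 = 24 nominal strata, and 708 / 24 = 29.5 patients on average, or 29.5 / 8 = 3.7 blocks. Equal strata of 30 are assumed below.
2. A block of 8 has C(8,4) = 70 equally likely sequences. An allocation is certain once one arm's four places are used up. The chance of this is 2/70 at the fifth place, 10/70 at the sixth, 30/70 at the seventh and 70/70 at the eighth. The sum is 112/70 = 1.6 of 8, or 20%.
3. With 30 patients there are three complete blocks plus six places of a fourth: 3 × 1.6 + 2/70 + 10/70 = 4.97, and 4.97 / 30 = 16.6%.
4. Always guessing the arm that is behind is right m + (4^m / C(2m,m) − 1) / 2 times in a block of 2m. For m = 4 this is 4 + (256/70 − 1) / 2 = 5.33 of 8, or 66.6%, against 50% by chance.
5. For comparison, fixed blocks of 6 and 4 give 25% and 33% certain in complete blocks.
6. With blocks drawn at random from 4, 6 and 8 (an illustrative mix, not from the protocol), a simulation of 4,000 strata of 30 patients gives 2.4% certain, even for an observer who knows the three sizes.
7. The simple guess does not improve. Correct guesses are 2.83 of 4, 4.10 of 6 and 5.33 of 8, so the equal mix gives (2.83 + 4.10 + 5.33) / 18 = 68.1%. Varying the sizes removes near-certainty, not guessing.

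Tracking is conceivable: the researcher approaches patients (10.2), and a researcher also phones intervention patients weekly (5.1).

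**The case against.** The case against is substantial.

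- The phrase about randomising during the measurements may simply mean at the baseline visit, and the person who randomises may not be the tester. This stands as a possible reading, but the text does not secure it.
- Encouragement in the 6MWT follows published guidelines (8.3), which limits the scope for staff influence. It does not remove it.
- A reader might infer that a patient's own allocation can affect that patient's enrolment. It cannot: agreement and written consent come first. Enrolment is exposed only through prediction, and allocation is by software.
- A reader might infer that patients will be excluded after randomisation, mostly from the exercise arm, and that intention-to-treat is thereby broken. The protocol does not support this. Section 5.1 describes triage of both arms, section 10.4 speaks of referral, section 8.5 rules out replacement, section 8.6 keeps all patients in regular follow-up, and section 9.6 sets an intention-to-treat analysis.
- A reader might take the Ferrara page to show training before the baseline is complete. It gives no order between allocation, tests and training; tests, then disclosure, then a first session at one visit would fit section 10.2.
- The 20 m in section 8.3 comes from measurement error and is not a between-arm effect, so it cannot size the bias.
- The block figures assume someone who tracks every earlier allocation in a stratum, and smaller fixed blocks would be worse.

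What remains is that the protocol states a weaker timing than it needs, leaves staff knowledge open, and discloses one fixed block size.

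**Conclusion.** The point holds as a weakness of concealment, not as demonstrated bias. As written, staff could know the arm before the baseline 6MWT is finished and before a contraindication to exercise is ruled in or out. The effect on the 6MWT comparison cannot be sized from the protocol.

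On predictability, a known fixed block of 8 makes 20% of allocations certain in complete blocks, and about 17% with 30 patients per stratum. Both figures are ceilings that assume full knowledge of earlier allocations in the stratum. That the trial is open is inferred from the nature of the arms and the absence of any stated masking. The improvement is worth making because it costs very little.

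**What to change.** 1. **Section 10.2.** Replace the sentence on timing with wording such as: *Randomisation takes place only after eligibility has been confirmed and all baseline measurements of that visit are complete.* If the timing cannot move, state at least that those who run the tests and judge fitness for exercise have no access to the result until then.
2. **Section 8.2.** Use randomly varying block sizes and keep the sizes in a document that sites do not hold. In the illustration this lowers the certain share from 16.6% to 2.4%; it does not lower the simple guess rate.
3. **Ferrara page.** Reconcile it with section 10.2 on the order of tests, allocation and first training session.

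The cost is a later allocation within the same visit, and occasionally later still if a test result needs follow-up. That matters somewhat given the five-week limit to surgery in section 10.2. Varying blocks could leave slightly more imbalance within strata if sizes above 8 are used; with sizes up to 8, an unfinished block can be at most 4 apart, as now. No extra visits or patients are needed.

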10.3 Objection by minors or incapacitated subjects (if applicable)

Not applicable.

10.4 Benefits and risks assessment, group relatedness

Patients in the prehabilitation group might benefit since they will be actively working on their physical and nutritional health status. No minors and incapacitated subjects will be included in the study, due to the impossibility to perform all exercises and fulfill all questionnaires. Side effects might be cardiac arrhythmias or other exercise related problems during the VO₂ maximal intensity exercise tests. Exercise training is not expected to cause any risk to patients. However, since patients are thoroughly screened, we expect to find more pre-existing cardio-pulmonary conditions, for which patients will be referred to either a pulmonologist or cardiologist. The amount of tests might be perceived as a burden for the patients in both groups, as well as the amount of hospital visits for the prehabilitation group.

10.5 Compensation for injury

The sponsor/investigator has a liability insurance which is in accordance with article 7 of the WMO.

The sponsor (also) has an insurance which is in accordance with the legal requirements in the Netherlands (Article 7 WMO). This insurance provides cover for damage to research subjects through injury or death caused by the study.

The insurance applies to the damage that becomes apparent during the study or within 4 years after the end of the study.

10.6 Incentives (if applicable)

Participants will not receive a standard financial compensation for participation as an incentive. However, they will receive travel compensation of 10 euro per visit to the hospital.

11. ADMINISTRATIVE ASPECTS, MONITORING AND PUBLICATION**11.1 Handling and storage of data and documents**

Data will be managed by an online data management system 'research manager'. Patients receive a unique study number, generated by the data management system. Study number is linked to patient details and stored in a secured file with password. Only the researcher and research nurse have access to this file. No human material will be collected.

11.2 Monitoring and Quality Assurance

Monitoring will be performed via a risk-based approach, as recommended by the FDA. Although monitoring is legally not required for this study, the sponsor (MMC) has decided to perform monitoring for all studies that fall under the scope of the WMO-act. Since this study has a minimal risk, monitoring should be performed annually and will partially be done centralized. Centralized monitoring is a remote evaluation carried out by sponsor personnel or representatives (e.g., clinical monitors, data management personnel, or statisticians) at a location other than the sites at which the clinical investigation is being conducted. Centralized monitoring processes can provide many of the capabilities of on-site monitoring as well as additional capabilities.

11.3 Amendments

Amendments are changes made to the research after a favorable opinion by the accredited METC has been given. All amendments will be submitted to the METC that gave a favorable opinion.

11.4 Annual progress report

The sponsor/investigator will submit a summary of the progress of the trial to the accredited METC once a year. Information will be provided on the date of inclusion of the first subject, numbers of subjects included and numbers of subjects that have completed the trial, serious adverse events/ serious adverse reactions, other problems, and amendments.

11.5 Temporary halt and (prematurely) end of study report

The investigator/sponsor will notify the accredited METC of the end of the study within a period of 8 weeks. The end of the study is defined as the last patient's last visit.

The sponsor will notify the METC immediately of a temporary halt of the study, including the reason of such an action.

In case the study is ended prematurely, the sponsor will notify the accredited METC within 15 days, including the reasons for the premature termination.

Within one year after the end of the study, the investigator/sponsor will submit a final study report with the results of the study, including any publications/abstracts of the study, to the accredited METC.

11.6 Public disclosure and publication policy

The trial is registered in the trial register under code NTR 5947

12. STRUCTURED RISK ANALYSIS

12.1 Potential issues of concern

Not applicable.

12.2 Synthesis

Not applicable.

13. APPENDICES

Appendix I

Table 1. Prehabilitation randomized controlled trial scheme

Weeks	Preoperative			Operation	Postoperative		
	-5 Before start	-4 Baseline	-1 Preoperative	0 Surgery	4 30 day follow up	8 8 weeks follow up	52 1 year follow up
Gastroenterologist	Inform patient	-	-	-	-	-	-
Sport physician	-	Informed consent VO2max Anaerobic threshold Exercise-ECG	VO2max Anaerobic threshold Exercise-ECG	-	VO2max Anaerobic threshold Exercise-ECG	-	-
Physiotherapist	-	6MWT Stair climb test Sit-to-stand test 1-RM test Activity questionnaire (derived from CHAMPS)	6MWT Stair climb test Sit-to-stand test 1-RM test Activity questionnaire	-	6MWT Stair climb test Sit-to-stand test 1-RM test Activity questionnaire	6MWT Stair climb test Sit-to-stand test 1-RM test Activity questionnaire	-
Dietician		Food diary (3 days) Height, weight Weight loss %* Wrist/abdominal/ Upper arm circumference Skinfold measurements Hand grip strength PG-SGA	Food diary (3 days) Height, weight Weight loss %* Wrist/abdominal/ Upper arm circumference Skinfold measurements Hand grip strength PG-SGA	-			-
Psychologist	-	Intake when indicated (details in protocol)	-	-	-	-	-
Anesthesiologist	-	-	Preoperative screening**	ERAS**	-	-	-
Surgeon	-	-	ERAS**	-	-	-	-
Surgical resident	-	-	-	-	Outpatient data	-	-
Researcher/ Case manager	Inclusion patient	Intake Coping with anxiety HRQoL GAD-7 PHQ-9 Fried Frailty Score G8 score	HRQoL GAD-7 PHQ-9 Program evaluation & health costs (brief)	-	Weight and weight loss %* Hand grip strength PG-SGA score 30-day morbidity and mortality HRQoL GAD-7 PHQ-9 Program evaluation Health costs	Weight and weight loss %* Hand grip strength PG-SGA HRQoL GAD7 PHQ-9	Mortality Activity questionnaire Health and life style HRQoL GAD-7 PHQ-9

Appendix II: Exercise training program

Detailed description of exercise training for the prehabilitation group.

[figure not shown]
¹ Endurance training, based on CPET data: VO₂peak/AT

² Resistance training, 1RM

³ Homework

Endurance training, based on CPET data (VO₂peak / AT)

- HIT = High intensity individualized interval training
 - o This supervised training will be done three times a week.
 - o The interval training duration is 28 minutes and performed with 4 intervals of Moderate intensity (3 minutes) and 4 intervals of High intensity (4 minutes). If the patient is unable to complete the high-intensity bout, the intensity is reduced by ten percent. The intensity is reduced further – in steps of ten percent – until the moderate activity level is performed if patients still cannot complete the bout. The remaining time of the bout will be continued at this level, after which the program will be completed as intended.
 - o The workload is dosed at a percentage of VO₂peak. High intensity is considered 90% of VO₂peak. Moderate intensity 90% of VO₂ AT.
 - o This interval training aims to reach levels of Borg 15-17 and >85% of the maximum heart rate (determined at the CPET), as long as the patient could effort the exercise.
 - o Exercise may be performed on a bicycle, a rower, a treadmill and/or on other aerobic exercise machines.

Resistance training, 1RM

- o This supervised training will be done three times a week.
- o Strength training will be the same concept for all patients irrespective of VO₂-peak.
- o The 1RM will be determined at baseline using: lateral pull down, leg press, chest press and abdominal crunch. The strength exercises are performed according to: 2 seconds of concentric strength and 2 seconds of eccentric strength. The 1RM is calculated by the Brzycki formula:
 - $1RM = W * 36 / (37 - r)$
 - W = weight in kilograms
 - r = repetitions
- o The strength training consists of two series of 10 repetitions of six exercises: leg press, chest press, abdominal crunch, lat pull down, low row and step up.
 - In week 1 using 65% of calculated 1RM (at baseline)
 - In week 2 using 70% of calculated 1RM
 - In week 3 using 75% of calculated 1RM
 - In week 4 using 75% of calculated 1RM
- o The last bout with 10 repetitions needs to be attainable. If this is not the case in the next session dosing will be 5-10% lower. If in the last bout it appears that exercises are too low (≥ 15 repetitions will be achieved), in the next sessions dosing will be 5-10% higher.

[figure not shown]
Homework/Counseling:

- The homework will be done at the days without supervised training, this will be a total of four days a week.
- Patients are instructed to aim at 60 minutes walking and/or cycling a day, but at least 30 minutes a day. If possible, patients can do more than 60 minutes of walking or cycling every day.
- Because of the low exercise capacity it is advised to walk/cycle 2-3 times a day for periods of 10-20 minutes.
- Also an electric bicycle, a stationary bicycle and/or a walking aid (walker) may be necessary.

Rest:

- Patients are instructed to take care of recovery and adequate rest and sleep.
- From 3 days before surgery no high intensive interval training and strength training are done. The patient will continue with the homework/counseling (walking/cycling every day) and the dietary supplements.

